8. RECRUITMENT

The majority of participants are expected to contact the study team after seeing study advertisements on social media or flyers posted in the community. Copies of IRB-approved study recruitment materials (e.g., flyers) may also be provided to clinic or school staff for them to share with potentially eligible participants; if interested, potential participants may then contact the study team to learn more. Once in touch with a study team member, potential participants will be provided with study information and their parent/caregiver will be assessed with an IRB-approved phone screen (see Telephone Screening Questionnaire). A waiver of written documentation of consent is requested for phone screening and retention of a password-protected “Subject Screen Log” that will contain child name, child age, parent name, parent email address and/or phone number, date of phone screen, and brief reason for likely eligibility or ineligibility. Retention of this information will be used by the study team to prevent from repeat screening of potential participants previously deemed ineligible or not interested, and to facilitate recontact for those who are eligible/interested but would like to participate at a later date. After the phone screen, potential subjects will proceed to signing a written consent (“enrolled”), followed by a detailed clinical assessment to confirm eligibility. If ineligible based on this assessment, the subject will be considered “withdrawn”; consent forms will be retained for those

withdrawn, but all other collected data will be destroyed except for reason for ineligibility and other information already contained in the Subject Screen Log.

Recruitment Settings at Columbia University:

The study team may provide approved recruitment materials to the following programs to share with potentially eligible participants:

CAPES Evaluation Service and the Youth Treatment and Evaluation of Anxiety and Mood (Y-TEAM) Program

The CAPES Evaluation Service and the Youth Treatment and Evaluation of Anxiety and Mood (Y-TEAM) Program is part of the Children's Day Unit at the New York State Psychiatric Institute. The CAPES/Y-TEAM provides free expert consultation, evaluation, and treatment referrals for children suffering from mood and anxiety disorders.

Morgan Stanley Children's Hospital of New York (CHONY)

Clinics at the Morgan Stanley Children's Hospital of New York (e.g., primary care Pediatrics, the Integrated Mental Health Program, School-Based Mental Health Program, and Pediatric Psychiatry Clinic).

Columbia University Center for Anxiety and Related Disorders (CUCARD) and Faculty Practice Organization (FPO)

CUCARD and the FPO sees 300 new children and adolescents per year referred for anxiety disorders. Clinic staff are experienced in providing families with information about potential research opportunities at Columbia University.

Private Practice

Mental health professionals who see children with anxiety disorders in private practice.

Primary Care Doctor's Offices and Clinics

Primary care clinics at CUIMC or identified through publicly available sources (i.e., websites, Google search). Initial outreach to provide study information to clinics is shared by email from research assistants to clinic leadership, copying [name], the study Principal Investigator, noting that she is available to address any questions/concerns (see email template, "Coordinator_to_Clinic_Email_Template_2.18.23").

Schools & Daycares

As with primary care clinics, preschool/kindergarten programs will be identified through publicly available sources (e.g., websites, Google search). Initial outreach to provide study information will be sent by research assistants to leadership at schools & daycares, copying [name], the study Principal Investigator, noting that she is available to address any questions/concerns (see email template, "Coordinator_to_Preschool_Email_Template_2.18.23").

Advocacy and Support Groups

Patient advocacy (e.g., International Obsessive Compulsive Disorder Foundation) and support groups (e.g, parent support groups).

Craigslist and Nextdoor

Craigslist website and on Nextdoor in local communities.

Social Media (e.g. Facebook, Twitter, and study-related websites)

An IRB-approved description of our study will be advertised on social media and relevant websites (e.g. departmental, Psychology Today). Facebook advertising may include groups of treatment providers, support group leaders, and parents or paid Facebook ads.

New York Family

New York Family runs a website (www.NewYorkFamily.com) and publishes regional print magazines that describe resources and activities for families in the NYC area. They also provide opt-in email targeting, where they send emails on the behalf of organizations and other companies to parents in NYC who have subscribed to their emails and who

have allowed third party partner promotions. InsideSchools is a project of the Center for New York City Affairs at The New School and runs a website (www.InsideSchools.org) that provides information about the NYC school system. New York Family sends newsletters to InsideSchools subscribers.

LinkedIn

LinkedIn to communicate with colleagues about our research efforts.

Google Ads

Google advertisements to advertise [name] recruitment webpage as one of the top search results for parents who make searches regarding pediatric anxiety in the NYC area.

RecruitMe:Columbia

Columbia University's RecruitMe, an online tool to connect potential research participants with researchers conducting relevant studies.

Flyers

Posted on bulletin boards in Columbia University Medical Center buildings as well as in local laundromats, grocery stores, public libraries, and community centers. Please see the attached flyers.

Recruitment Settings at Michigan State University:

None. The MSU site has completed recruitment and will not be enrolling any future participants.

9. INFORMED CONSENT

Prior to conducting the eligibility portion of the telephone screen, research staff will document verbal consent to proceed with the conversation in the Subject Screening Log. Additionally, a waiver of documentation of consent is requested for the phone screen.

Prior to initiating baseline clinical assessment procedures, research staff will obtain written consent from the participant's parent/legal guardian for themselves to participate in the study (parent informed consent) and for their child to participate in the study (parental permission). Research staff will describe the purpose and nature of the research study and answer any questions. Parents/legal guardians will receive signed copies of both the parent informed consent and the parental permission.

Informed consent is a process that is initiated prior to the potential child subject's parent agreeing to participate in the study and continues throughout the individual's study participation. Extensive discussion of risks and possible benefits of this intervention will be provided to the parent/legal guardian, including risks related to travel for in-person visits during COVID-19. The parent will be made aware that the study team requests they not initiate other treatment for their child's anxiety during their participation in this study. It will be made clear that this study is voluntary, so they are free to seek other treatment for their child at any point if they feel it is needed. If they are considering said additional treatment, the researcher obtaining consent will request that they discuss this with the study team first, and may need to be withdrawn from the study as a result.

Consent for remote clinical or research procedures will be documented, and the consent discussion process will include discussion of the technology HIPAA-compliant platforms to be used and any concerns the patient may have, such as access to a private space in which to take calls, or accessibility—access at home to adequate devices, cell signal, or internet.

Consent forms (written in non-technical language, understandable by the parent of the participant to be enrolled in the study) describing in detail the study interventions, procedures, and risks will be given to the parent. Upon reviewing the documents, one of the investigators (or their designee) will explain the research study to the subject/parent and answer any questions that may arise.

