4. SPECIFIC AIMS/HYPOTHESES

Aim 1: Confirm that Kidpower-Structured Games engages neural and behavioral markers of EC. We hypothesize that Kidpower-Structured Games will produce greater increases in neurophysiological and behavioral markers of EC than Kidpower-Child-Led Play (CLP, active comparator).

Aim2: Assess the relationship between pre- to post-Kidpower-Structured Games change in neurobehavioral markers of EC and change in clinically significant anxiety. We hypothesize that increases in neurophysiological and behavioral measures of EC will relate to reductions in clinically significant anxiety from pre-to-post Kidpower- Structured Games. Exploratory analyses will examine the moderating effects of baseline threat reactivity on the relation between pre- to post-treatment increase in EC and reduction in anxiety severity.

Aim 3: Explore dosing effects of Kidpower-Structured Games on behavioral EC targets and anxiety symptoms. We hypothesize that greater at-home practice of Kidpower-Structured Games exercises will relate to greater engagement of neural and behavioral markers of EC targets and greater reduction in anxiety symptoms. Dosage will be assessed by weekly parent report on child practice of EC exercises at home (frequency, duration).

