Participants are randomized to a camp-style intervention ("Camp Kidpower"), which includes either EC training (Kidpower-Structured Games) or child-led playgroup (active comparator; Kidpower-CLP). Before and after the 4-week intervention, a multi-level assessment will be completed, including clinical interview with parent about their child's anxiety symptoms, parent-report surveys on child and self, lab-observed behavioral tasks and electroencephalogram (EEG) with child. Primary analyses will test for group mean differences in neurophysiological and behavioral indices of EC from time 1 (pre-intervention) to time 2 (post-intervention) among children assigned to Kidpower- Structured Games training compared to those assigned to Kidpower-CLP. Secondary analyses will test relationship of changes in neurophysiological targets with change in EC behaviors and change in anxiety severity.

The Kidpower-Structured Games were adapted from a group-based intervention originally designed to treat EC deficits in children with attention deficit hyperactivity disorder (Halperin et al, 2013) and a recently published review of executive function and effortful control interventions (Diamond and Ling, 2016). Kidpower-CLP was developed by the study team to include all of the same elements as Kidpower-Structured Games except for EC training games.

Both Kidpower-Structured Games and Kidpower-CLP will occur over 4-5 sessions, for approximately 3 hours each session. Sessions may be delivered back-to-back or over the course of four weeks. Times will be chosen to maximize child focus and energy and to provide the most convenience for families. Regardless of condition, children will begin with a group welcome activity, then will complete 1-2 of the intervention exercises for that day with their camp counselor. After a brief break and snack, children will complete the remaining 1-2 intervention exercises with their camp counselor, then come back together for a final group activity. The last 30 minutes of camp will include parents, who will be assigned daily homework involving the same play as at camp to complete with their child in between camp sessions. Two parent meetings (led by the lead camp counselor) will take place; the first will occur prior to the beginning of camp to orient parents, and the second will be held mid-way through camp to answer questions that may have arisen.

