2. Participants may experience some discomfort upon removal of the electrophysiological equipment – specifically, facial electrode sensors.

To minimize risk: Participants will be informed that facial electrode sensors are similar to Band- Aids, to help guide their preference for removal.

Risks Associated with Behavioral Battery

1. Some children may experience some emotional discomfort or apprehension when engaging in the behavioral "potential threat task." During this task, children enter a room and are asked to approach a covered terrarium. When they get close, the cover is lifted by the experimenter to reveal a benign object (e.g., a tissue box). This task elicits uncertainty during approach.

To minimize risk: Particular care will be taken during debriefing of the potential threat task. Child participants will be reassured that the covered object is not threatening immediately after its presentation. If a child becomes overly distressed, the protocol may be interrupted and parent can interact with child to provide comfort. The task may be

ended early if the child becomes tearful or otherwise highly distressed. All participants will be given a 5-minute free play with the parent immediately after the fear task to regulate and debrief.

Risks Associated with Intervention Training

1. Risks of participating in the camp are minimal, and include boredom or frustration with training tasks, similar to experiences children may encounter in a day-to-day school environment.

To minimize risk: Participants will be allowed breaks throughout daily training. Study team members conducting the camp will have experience with young children and be closely supervised by [name].

2. As with any group activity with children, there is always the possibility of unpredictable behavior, which could cause children discomfort or distress.

To minimize risk: Every precaution will be taken to ensure the safety of all children participating in the camp. This includes reserving the right to ask children to discontinue participation if there is reasonable concern for unsafe behavior.

Risks Associated with COVID-19

1. Travel to CU for the onsite sessions may increase risk of exposure to COVID-19.

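### Section 9 allows study withdrawal when a family considers other treatment and does not secure time-2 data, which could attenuate the Aim 2 association and slightly bias the EC arm contrast

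*Combined protocol and SAP*

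**What the plan says.** Section 9 makes three statements about other treatment. First, "the study team requests they not initiate other treatment for their child's anxiety during their participation in this study". Second, parents are told that "they are free to seek other treatment for their child at any point if they feel it is needed". Third, if they are considering it they are asked to talk to the study team first, and they "may need to be withdrawn from the study as a result". The section does not say who decides or on what criteria.

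Section 11 (Risk Minimization), under the risks of intervention training, adds a further route out: "reserving the right to ask children to discontinue participation if there is reasonable concern for unsafe behavior". It does not mention the time-2 visit.

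The analyses that need time-2 data are these:

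- **Primary analysis (section 6, Research Design and Methods).** Change in EC indices from before to after the intervention is compared between arms. On timing: "Before and after the 4-week intervention, a multi-level assessment will be completed".
- **Aim 2 (section 4).** Within Structured Games, the hypothesis is that "increases in neurophysiological and behavioral measures of EC will relate to reductions in clinically significant anxiety".

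The supplied text contains no statement on assessing or analysing a randomised child who is withdrawn, and no analysis set, missing-data method or dropout assumption.

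**The concern.** Whether a parent looks for other treatment is settled after randomisation and plausibly depends on how the child is doing. If such a child leaves the study and not just the camp, the time-2 values go too, and the children who remain are partly selected on outcome.

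Aim 2 is the more exposed analysis. Selection acts directly on anxiety change, which is one of the two variables being related. Losing children at the poorly improving end narrows its range and weakens any true association.

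The primary contrast is exposed only indirectly, because its outcome is EC and not anxiety. Bias there needs EC change to be correlated with anxiety change, together with either a true arm effect or withdrawal that differs by arm. The trial's own hypothesis supplies the first condition and a true arm effect, since it holds that EC training improves EC and thereby reduces anxiety. Time-2 data that were never collected cannot be recovered at analysis.

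**Working it through.** **1. No figure to reproduce.** The documents state no alpha, power, effect size, SD, allocation ratio or dropout rate. Everything below illustrates size under stated assumptions.

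**2. Inputs from the documents.** Section 6 pools Michigan State (71), New York State Psychiatric Institute (43) and up to 20 at Columbia: 71 + 43 + 20 = 134 at most. With 1:1 allocation (assumed) that is 67 per arm.

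**3. Yardstick.** For a two-sided 5% test with 80% power, the detectable difference is (1.960 + 0.842) × √(2/67) = 0.48 SD. With 5%, 10% or 20% of children lost it becomes 0.50, 0.51 or 0.54 SD.

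**4. Model.** There were 2,000,000 simulated children per scenario, allocated 1:1.

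- EC change: E = δ × arm + noise with SD 1.
- Anxiety improvement: A = ρE + noise. Without selection the runs return correlations of 0.30 and 0.50 for ρ = 0.3 and 0.5.
- Withdrawal is logistic in A, with the odds multiplied by 1, 2 or 4 for each SD less improvement.
- Withdrawn children have no time-2 data, and completers are analysed.
- Assumed values: δ = 0 or 0.5; ρ = 0, 0.3 or 0.5; overall withdrawal 5%, 10% or 20%.

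**5. EC arm contrast, same mechanism in both arms (odds ×4, δ = 0.5).** Bias in SD:

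| Withdrawn | ρ = 0.3 | ρ = 0.5 |
|---|---|---|
| 5% | -0.001 | -0.010 |
| 10% | -0.004 | -0.013 |
| 20% | -0.008 | -0.024 |

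The largest value turns a true 0.500 into 0.476. With δ = 0 or ρ = 0 the bias is zero apart from simulation noise.

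**6. EC arm contrast, withdrawal also differing by arm.** The odds in Structured Games are multiplied by a further 1/3, still with odds ×4 per SD. Bias in SD:

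| Overall withdrawn | δ | ρ = 0.3 | ρ = 0.5 |
|---|---|---|---|
| 10% | 0.5 | -0.030 | -0.056 |
| 20% | 0.5 | -0.049 | -0.083 |
| 10% | 0 | -0.026 | -0.040 |
| 20% | 0 | -0.037 | -0.066 |

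Withdrawal in Structured Games against the comparator was about 5-6% against 14-15%, and 11-13% against 27-29%. The sign is negative because the comparator was assumed to lose more children. With δ = 0 it reverses, by symmetry, if Structured Games loses more. With ρ = 0 the EC bias is again zero.

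**7. Aim 2 (Structured Games arm, odds ×4, no arm effect on withdrawal).**

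| Withdrawn | r, true 0.30 | slope, true 0.30 | r, true 0.50 | slope, true 0.50 |
|---|---|---|---|---|
| 5% | 0.29 | 0.28 | 0.49 | 0.48 |
| 10% | 0.28 | 0.27 | 0.48 | 0.46 |
| 20% | 0.27 | 0.25 | 0.47 | 0.44 |

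There is no bias if ρ = 0 or if withdrawal is unrelated to improvement.

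**8. Aim 2 power.** Power = Φ(atanh(r) × √(n - 3) - 1.96).

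- r = 0.30, n = 67: Φ(0.310 × 8.00 - 1.96) = 0.70.
- r = 0.30, n = 60 (about 10% lost): Φ(0.310 × 7.55 - 1.96) = 0.65.
- r = 0.28, n = 60: Φ(0.288 × 7.55 - 1.96) = 0.58.

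Of the fall from 0.70 to 0.58, about 0.05 is lost sample size and about 0.07 is attenuation.

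**9. Reach of a change to the visit rule.** Michigan State has completed enrolment, so new wording mainly protects the Columbia children: 20/134 = 15% of the pooled maximum. If 20% of them were withdrawn, that is 4 children, or 4/134 = 3.0% of the pool.

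**The case against.** The case on the other side has real weight.

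- **Withdrawal is discretionary.** Section 9 says it may be needed. No counts or reasons are given, and preferential loss of children who are not improving is an inference from parent-perceived need. This stands, so the point is about what could happen.
- **A mechanism study has reason to limit co-treatment.** Section 7 excludes current psychotherapy and medication acting on the central nervous system, and co-treated children could blur the link between EC and anxiety. This is a fair reason for reporting Aim 2 without them as well. It is no reason not to collect their data.
- **Both arms are active and the window is short.** Staff-to-child ratios match, parents in both arms have homework, and the intervention takes about four weeks. Differential loss need not be large.
- **Section 11 most naturally concerns camp.** Its sentence sits under the risks of the camp, and section 7 already excludes recent harmful aggression. It needs only a clarification that stopping camp does not end assessment.
- **Some consent text is not in the public copy.** The absence noted here is absence from the supplied text.

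Two stronger readings are tempting. A reader might infer from section 8 that a withdrawn child's data are destroyed, since it says "all other collected data will be destroyed except for reason for ineligibility". That sentence covers only children found ineligible at the clinical assessment. A reader might also infer a substantial rise in false-positive arm differences. That requires the worst-faring children to be removed from one arm only and anxiety to be the between-arm outcome. The documents do not suggest such one-sided loss, and their primary contrast is on EC.

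**Conclusion.** The point holds as a gap that should be closed. Section 9 permits withdrawal from the whole study for a reason that may be related to outcome, and the supplied text secures neither the time-2 visit nor analysis in the assigned arm.

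The likely consequence is modest attenuation in Aim 2 and a small possible bias in the EC contrast. The largest EC bias in the scenarios tried, 0.083 SD, is about 17% of the 0.48 SD detectable difference (0.083/0.48). The largest under a shared mechanism, 0.024 SD, is about 5% (0.024/0.48).

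These sizes depend on assumed withdrawal rates, on a fourfold rise in the odds of withdrawal per SD less improvement, and on EC and anxiety change correlating at 0.3 to 0.5. The documents do not support saying that either analysis is in fact biased. Nor do they show whether the rule was used among the 114 children at the other two sites, although section 6 describes the protocol there as the same.

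**What to change.** 1. **Section 9, and section 11 for camp discontinuation.** Separate stopping camp from leaving the study. Possible wording: *A child who stops attending camp, or whose family starts or considers other treatment, remains in the study for assessment unless the parent withdraws consent, and will be invited to the time-2 visit.* This applies to every randomised child whose time-2 visit is still ahead.
2. **Section 6.** State that all available randomised children, at all pooled sites, are analysed in the arm to which they were assigned.
3. **Data collection.** Record the date and type of any other treatment, and report withdrawals and their reasons by arm. Where site records allow, do this for the two other sites too.
4. **Aim 2.** Report the association with and without co-treated children.

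The cost is protocol and consent wording and a few extra time-2 visits. Some time-2 scores will reflect other treatment, and the two Aim 2 analyses will show how much that matters. Parents' freedom to seek care, and decisions about care and camp attendance, are unchanged.

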10. PRIVATE, IDENTIFIABLE INFORMATION ABOUT RESEARCH PARTICIPANTS

We collect the following identifiable information: Parent name, child name, parent date of birth, child date of birth, parent email address, parent cell phone number, parent city of birth, child city of birth.

To ensure adequate protection of human subjects, the investigators and research staff will complete human subjects training as required by their respective institutions (e.g., CITI Training at CU). Every possible effort will be made to limit identifiable information on potential subjects during recruitment. The minimum amount of necessary information will be recorded, and staff are aware of the dangers of emailing, printing, and faxing sensitive information. Conversations in which a patient or participant's name must be mentioned (e.g., determining study eligibility) will occur in private settings. Phone calls with potential research subjects will occur behind closed doors. Remote visits will be conducted via HIPAA-compliant video teleconferencing to protect confidentiality, all in accordance with the CU Remote Communications Guidance.

During camp, children will only be addressed by first name (or first initial if desired by family and the child is responsive to this option) to help protect participant privacy.

Privacy of each parent and child's clinical research information will be protected and only reviewed by the PI and study staff. Mandatory reporting of child abuse and neglect (e.g., detected in surveys, reported in interviews) is required in accordance with clinical standard practice. If a study team member learns that a subject has the potential to harm him or herself, or another individual, we will break confidentiality and take steps to prevent harm. Similarly, any evidence of potential child abuse will be reported to Child Protective Services. Mandatory reporting is explained to subjects in the informed consent document as a limit to confidentiality.

In all records from this study, the names of participants and their family members will be available only to the team of researchers working on the study. Neither their names nor any identifying information will be used in any scientific reports from this study or from secondary data analyses conducted with de-identified data from this study. Participants will be assigned a unique coded subject identification number and their names will not be on any study materials. We will use the study data only for scientific, education, or instructional purposes. To ensure confidentiality, the master list of identifying information needed for participant contact, such as names, addresses, and telephone numbers, will be kept in a password-protected and encrypted database. All virtual information is saved on password-protected computers, and all email communication is secure and encrypted. The computing systems are protected from outside access by firewall systems. Paper records are kept in file drawers in a locked room and paper records with identifying information (e.g., payment records) are kept in locked file cabinets physically separate from the research records. Only authorized research personnel will have access to the locked rooms in which these records are contained.

All questionnaire and task responses, including data from the data from clinical interviews will be kept confidential, and will only be marked with subject ID numbers. An electronic database will be used to store the coded data, and the key linking to identifiable subject information will be kept separate from the database with research data. This coded data will be stored using MSU Qualtrics which is a secure, HIPAA- compliant application. Access to Qualtrics requires authorization and the study's database is encrypted and password-protected (see Data Management Plan for details).

Mandatory reporting of child abuse and neglect (e.g., detected in surveys, reported in interviews) is required in accordance with clinical standard practice. If a study team member learns that a subject has the potential to harm him or herself, or another individual, we will break confidentiality and take steps to prevent harm. Similarly, any evidence of potential child abuse will be reported to Child Protective Services. Mandatory reporting is explained to subjects in the informed consent document as a limit to confidentiality.

